7.2. Number of Subjects

One hundred and fifty subjects will participate in the study.

7.3. Treatment Assignment

Subjects will be randomized 1:1 to either ecopipam or matching placebo. Randomization assignment will be stratified by weight.

7.4. Dose Adjustment Criteria

Doses will be titrated up to and down from the target dose based on the subject's weight at Baseline according to the following weight bands to better achieve the targeted 2 mg/kg/day target dose: ≥ 18 to ≤ 23 kg, ≥ 23 to ≤ 34 kg, ≥ 34 to ≤ 44 kg, ≥ 44 to ≤ 68 kg, ≥ 68 to ≤ 83 kg, ≥ 83 kg. Those who cannot tolerate the target dose will be withdrawn from study. Weight band assignments will not change during the duration of the study. See Section 10.5 for direction on administration of study drug.

7.5. Criteria for Subject Study Discontinuation

A subject may elect to discontinue from the study at any time for safety or personal reasons. All subjects who discontinue from the study should complete the early study discontinuation procedures.

Any subject with a new positive response on questions 4 and/or 5 of the Columbia Suicide Severity Rating Scale (C-SSRS) will be immediately discontinued and evaluated for risk. Dosing may be restarted at the discretion of the Investigator following consultation with the Sponsor or its designee.

Subjects who discontinue early from the study will be evaluated for one of these primary reasons: AE(s), lost to follow-up, subject choice, inadequate therapeutic effect, and administrative/other. In addition to the primary reason, the subject may have indicated one or more of these reasons as secondary reasons for discontinuation. Study disposition information will be collected on the CRF.

Subjects who discontinue treatment for any reason, other than an SAE (even if the SAE is not treatment related) or an AE (unless the AE can be determined to be unrelated to treatment), may be replaced only after consultation with Sponsor or its designee.

Table 2:Schedule of Assessments

Assessment	Screening ^a	Baseline	Titra	ition	Т	freatmen	ıt	Completion/ Early Termination	7 Day Follow-up	14 Day Follow-up	30 day Follow-up*
Study Week	Up to -4	0	2*	4 ^g	6 ^g	8 ^g	10*	12 ^g	13/14 ^g	14/15 ^g	16/17
Study Days	Up to -28	0	14 + 3	28 + 3	42 + 3	56 + 3	70 + 3	84 + 3	7 Days Post Last Dose + 3	14 Days Post Last Dose + 3	30 Days Post Last Dose + 3
Study Visit Number	1	2	3	4	5	6	7	8	9	10	11
Informed Consent	Х										
Inclusion/ Exclusion	Х	Х									
Medical/Psychiatric/medicat ion History	Х	Х									
Randomization		Х									
Physical Exam/Vital Signs ^b	Х	Х		Х	Х	X		X	Х	Х	
ECG	Х	Х		Х	Х	Х		X	Х	Х	
Laboratory tests (Hematology and Chemistry) ^c	х	Х						Х	Х	X°	
Urine Drug Screen	Х	Х						X			
Urine Pregnancy Test	Х	Х						X		Х	
DSM-5 Criteria for TS	Х										
Yale Global Tic Severity Scale	Х	Х		Х	Х	Х		Х			
Clinical Global Impression - Tourette's Syndrome of Severity		Х		X	Х	X		Х			
Clinical Global Impression - Tourette's Syndrome of Improvement				X	X	X		Х			

Assessment	Screening ^a	Baseline	Titra	ition	Т	reatmen	ıt	Completion/ Early Termination	7 Day Follow-up	14 Day Follow-up	30 day Follow-up*
Study Week	Up to -4	0	2*	4 ^g	6 ^g	8 ^g	10*	12 ^g	13/14 ^g	14/15 ^g	16/17
Study Days	Up to -28	0	14 + 3	28 + 3	42 + 3	56 + 3	70 + 3	84 + 3	7 Days Post Last Dose + 3	14 Days Post Last Dose + 3	30 Days Post Last Dose + 3
Study Visit Number	1	2	3	4	5	6	7	8	9	10	11
Caregiver Global Impression of Change				Х	Х	Х		Х			
Columbia Suicide Severity Rating Scale	Х	Х	Х	Х	Х	Х	Х	Х	Х	X	
Abnormal Involuntary Movement ^d		Х		Х	Х	Х		Х			
Barnes Akathisia Rating Scale		Х		X	Х	Х		Х			
Swanson, Nolan, and Pelham Questionnaire		Х		Х	Х	Х		Х			
Children's Yale-Brown Obsessive Compulsive Scale		Х		Х	Х	Х		Х			
Children's Depression Rating Scale - Revised		X		X	Х	X		Х			
Gilles de la Tourette Syndrome Quality of Life Scale		Х		X	Х	Х		Х			
Pediatric Anxiety Scale		Х		Х	Х	Х		Х			
PK Blood Draws ^{e,h}				Х				Х			
Adverse Events	Х	Х	Х	Х	Х	Х	Х	Х	Х	Х	X*
Concomitant Medications	Х	Х		Х	Х	Х		Х	Х	Х	
Dispense Study Drug		Х		Х	Х	Х		X ^f			

Assessment	Screening ^a	Baseline	Titra	tion	Т	reatmen	t	Completion/ Early Termination	7 Day Follow-up	14 Day Follow-up	30 day Follow-up*
Study Week	Up to -4	0	2*	4 ^g	6 ^g	8 ^g	10*	12 ^g	13/14 ^g	14/15 ^g	16/17
Study Days	Up to -28	0	14 + 3	28 + 3	42 + 3	56 + 3	70 + 3	84 + 3	7 Days Post Last Dose + 3	14 Days Post Last Dose + 3	30 Days Post Last Dose + 3
Study Visit Number	1	2	3	4	5	6	7	8	9	10	11
Collect Unused Study Drug/Assess drug compliance				Х	Х	Х		Х	Х		

Abbreviations: AE = adverse event; BP = blood pressure; ECG = electrocardiogram; HR = heart rate; PK = pharmacokinetic(s)

^a Informed consent must be performed prior to any screening procedures. All screening procedures are to occur after washout of any applicable medications. Rescreening is allowed after approval by the Medical Advisor.

^b Vital signs will include, pulse, BP, orthostatic BP (done 5 minutes after being supine and then 3 minutes after standing), height and weight.

^c Subjects should be in a fasting state (8 hours) for laboratory tests. HbA1c will be measured at the baseline and completion/early termination visits.

^d Every attempt should be made to perform this assessment at the same time at each visit.

^e At Week 4 Study dose should not be taken until after pre-dose blood draw at the site. PK draws should be pre-dose, between 0.5 and 1.5 hours after study drug administration, and between 2 and 4 hours after study drug administration. Both Week 4 and Week 12, visits should be scheduled for the morning. At Week 12, blood sample will be collected in the afternoon at the end of the visit.

^f Study drug will be dispensed for dose down titration.

* Weeks 2 and 10 will be telephone visits. If there are any abnormal findings, the subject will be brought to the site for full assessment. A telephone call will be made to the subject 30 days after the last dose to assess any adverse events that may have occurred.

^g Assessments for these visits may be completed in locations other than study clinic and/or safety and efficacy assessments required at these visits will be made available for remote administration due to restrictions as a consequence of the COVID-19 pandemic or other qualifying event.

^h If visits at Weeks 4 and 12 are completed in locations other than study clinic due to restrictions as a consequence of the COVID-19 pandemic or other qualifying event, then collection of labs for PK assessments are optional

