8.2. Exclusion Criteria

Individuals meeting any of the following criteria at Screening or Baseline are ineligible to participate in the study:

1) Subjects with any unstable primary mood disorder (DSM-5 criteria) at Screening.

- 2) Subjects who have unstable medical illness or clinically significant abnormalities on laboratory tests, or ECG at Screening as determined by the Principal Investigator.
- 3) Subjects with a significant risk of committing suicide based on history, routine psychiatric status examination, investigator's judgment, or who had an answer of "yes" on any question other than 1–3 (currently or within the past 30 days) on the baseline/screening version of the C-SSRS.
- 4) Subjects with a clinical presentation at Screening and/or history consistent with another neurologic condition that may have had accompanying abnormal movements (e.g., Huntington's disease, Parkinson's disease, Wilson's disease, stroke, Restless Legs Syndrome).
- 5) Female subjects who are currently pregnant or lactating or planning to become pregnant during the course of the study.
- 6) Subjects who have moderate to severe renal insufficiency at Screening.
- 7) Subjects who have hepatic impairment at Screening.
- 8) Subjects with current or recent (past 3 months) history of DSM-5 substance use disorder (with the exception of nicotine).
- 9) Subjects with positive urine drug screen for cocaine, amphetamine, methamphetamine, benzodiazepines, barbiturates, phencyclidine (PCP) or opiates at Screening except those receiving stable, prescribed treatment for ADHD.
- 10) Subjects with \geq 25% absolute change in YGTSS-TTS score between the Screening Visit and Baseline visit assessments.
- 11) Subjects with a lifetime history of bipolar disorder type I or II, dementia, schizophrenia, or any other psychotic disorder.
- 12) Subjects with a major depressive episode in the past 2 years.
- 13) Subjects with a history of attempted suicide.
- 14) Subjects with a history of seizures (excluding febrile seizures that occurred <2 years prior to Screening).
- 15) Subjects with history of neuroleptic malignant syndrome.
- 16) Subjects with a myocardial infarction within 6 months.
- 17) Subjects who have had previous treatment with ecopipam.
- 18) Subjects who have had previous treatment with:
 - a. investigational medication within 1 month prior to Screening
 - b. depot neuroleptics within 3 months prior to Screening
 - c. oral neuroleptics within 4 weeks prior to Screening

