8.3. Subject Withdrawal, Removal, and Replacement Criteria

Any subject with a CDRS-R assessment indicative of the onset of a new depressive episode at any visit can be discontinued from study participation at the discretion of the Investigator. Any subject with a new positive response on questions 4 and/or 5 of the C-SSRS will be immediately discontinued and evaluated for risk. Dosing may be restarted at the discretion of the Investigator following consultation with the Sponsor or its designee.

The Investigator or subject may choose to stop study treatment at any time for safety or personal reasons.

Where possible, a subject who discontinues treatment will undergo protocol-specified end-of study procedures at the time of discontinuation. Date and reason(s) of premature discontinuation will be described in the CRF. In addition, the date of last dose of study treatment will be recorded on the Study Treatment Dosing CRF.

Subjects who discontinue treatment for any reason, other than an SAE (even if the SAE is not treatment related) or an AE (unless the AE can be determined to be unrelated to treatment), may be replaced only after consultation with Sponsor or its representative.

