12.1.1. Columbia Suicide Severity Rating Scale

An additional assessment will include the Columbia-Suicide Severity Rating Scale (C-SSRS) (all Visits except the 30-day Follow-up visit).

The C-SSRS is a low burden (approximately 5 minutes for completion) instrument to assess both suicidal behavior and ideation. The scale is appropriate for subjects from age 6 through to an elderly population.

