10.8. Columbia Suicide Severity Rating Scale (C-SSRS)

The C-SSRS is a low burden (approximately 5 minutes for completion) instrument to assess both suicidal behavior and ideation. The scale is appropriate for subjects from age 6 through to an elderly population.

The number and percentage of subjects with suicidal behavior and ideation will be summarized by treatment group at the Baseline, Week 4, Week 6, Week 8 and Week 12 visits and all questionnaire data will be displayed in a listing.

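### The mandatory suicidality stop is tied only to C-SSRS questions 4 and 5; no rule requires stopping after new suicidal behavior or an attempt on study

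*Protocol*

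**What the plan says.** **The mandatory rule.** Protocol 7.5 states: "Any subject with a new positive response on questions 4 and/or 5 of the Columbia Suicide Severity Rating Scale (C-SSRS) will be immediately discontinued". Section 8.3 has the same rule: "Any subject with a new positive response on questions 4 and/or 5 of the C-SSRS will be immediately discontinued and evaluated for risk". In both places the next sentence lets the investigator restart dosing after consulting the sponsor or its designee.

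**The discretionary rules.** Section 8.3 adds a general safety stop: "The Investigator or subject may choose to stop study treatment at any time for safety or personal reasons". It also has a depression rule based on the Children's Depression Rating Scale (CDRS-R): "Any subject with a CDRS-R assessment indicative of the onset of a new depressive episode at any visit can be discontinued". That rule is likewise at the investigator's discretion.

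**Behavior elsewhere in the plan.** Exclusion 13 in Protocol 8.2 bars "Subjects with a history of attempted suicide". Protocol 12.1.1 describes the C-SSRS as an "instrument to assess both suicidal behavior and ideation". SAP 10.8 says: "The number and percentage of subjects with suicidal behavior and ideation will be summarized by treatment group".

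**The concern.** The plan treats suicidal behavior as important when it decides who may enter, what is measured and what is tabulated. It does not do so when it lists what must stop dosing. A past attempt keeps a child out of the trial, but an attempt while on study drug does not by rule stop the drug. The risk evaluation and the consultation before restart are tied to the question 4 or 5 trigger, so they are not required after such an event either.

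The subjects are children aged 6 to 17, and the protocol gives grounds for a firm suicidality rule. Section 5.2.2.1 says the adult Phase 3 obesity studies were discontinued for psychiatric adverse events (31% on ecopipam, 15% on placebo) that included suicidal ideation. Section 5.3.1 says suicidal ideation was seen in the earlier blinded pediatric study and in its open-label extension. Against that, 5.2.2.1 reports no evidence that ecopipam affected the C-SSRS in the pediatric study. All of this evidence concerns ideation. It supports having a rule, and does not by itself show that behavior is the missing part.

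**Working it through.** No figure in the plan bears on this point, so the check is a reading of the text. Every provision that could stop a subject's drug, or that deals with suicidality, is set out below.

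| Provision | What sets it off | Must study drug stop? |
|---|---|---|
| Protocol 7.5 and 8.3, C-SSRS rule | New positive question 4 and/or 5 | Yes, with risk evaluation, and consultation before restart |
| Protocol 7.4 and 10.5 | Dose or titration not tolerated | Yes, but unrelated to suicidality |
| Protocol 8.3, general safety stop | Judgment of investigator or subject | No |
| Protocol 8.3, CDRS-R rule | New depressive episode | No |
| Protocol Table 2, telephone-visit footnote | Abnormal finding at Week 2 or 10 | No; site assessment only |
| Protocol 12.2.1.2 and 12.5 | Event meeting the definition of serious | No; report within 1 business day |
| Protocol 13.2.4 and 13.2.5, monitoring board | Review at the interim analysis | No; recommendations on the trial |
| SAP 10.8 | Suicidal behavior or ideation on the C-SSRS | No; summary table |

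The telephone footnote reads: "If there are any abnormal findings, the subject will be brought to the site for full assessment". It brings the child in but sets no dosing consequence.

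**Step 1.** Of the mandatory stops, only the C-SSRS rule concerns suicidality, and it names two question numbers. None names suicidal behavior or an attempt.

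**Step 2.** Compare two children. One attempted suicide before screening and is excluded by criterion 13. The other makes an attempt on study that is reported as an adverse event, without a new positive question 4 or 5. For the second child, 7.5 and 8.3 require no stop, no risk evaluation and no consultation before dosing continues. A serious adverse event report would inform pharmacovigilance, but nothing ties that report to a dosing decision.

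**Step 3.** Is the information already collected? Table 2 schedules the C-SSRS at eight post-baseline visits: Weeks 2, 4, 6, 8, 10 and 12 and the 7-day and 14-day follow-ups. The two follow-ups come after the last dose, which leaves 8 − 2 = 6 visits at which a stop could act. At Week 12 only taper doses remain. Adverse events are collected throughout. A wider trigger therefore needs no new data.

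**Step 4.** Can the gap be sized? The documents give no rate of behavior with questions 4 and 5 negative. If that rate were p, the expected number among 150 subjects would be 150p and the chance of at least one would be 1 − (1 − p)^150. Taking p from 0.1% to 2%, purely as an assumption, gives 0.15 to 3 subjects and a chance of 14% to 95%. That range covers nearly every outcome, has no anchor in the documents and pools both arms. It also ignores subjects whom an investigator would stop anyway. It shows that the gap cannot be sized from these documents, so the conclusion does not use it.

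**The case against.** The strongest reply is that the gap may be small in practice. An investigator may stop drug for safety at any time, and most would probably do so after an attempt. Serious events, including important medical events that may put the subject in jeopardy, must be reported within 1 business day. The C-SSRS is repeated at every visit except the 30-day call. Even the mandatory stop is reversible, so the change turns a discretionary stop into a mandatory but reversible one. All of this stands. It narrows the gap without closing it, because none of these provisions obliges anyone to stop the drug, evaluate risk or consult before the next dose.

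A second reply is that a child with new behavior might also answer question 4 or 5 positively, which would trigger the existing rule. That may be so. The documents do not print the C-SSRS items, so they show neither that this would always happen nor how often it would fail.

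A reader might infer more than the text supports:

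- **That questions 4 and 5 cover ideation only, so every attempt escapes the rule.** The items are not in the documents. The point rests on what the rule names, and nothing is drawn from the question numbers or from exclusion 3.
- **That the protocol lets a child stay on drug after an attempt as a matter of policy.** It is silent on a required stop and permits one.
- **That the SAP and protocol disagree because only the SAP lists suicide and self-injury as an adverse event of special interest.** The protocol's sentence in 12.2.1.3 is worded as a non-exhaustive list and sets no site action. The SAP list feeds summary tables. Neither bears on stopping drug.
- **That ecopipam has been shown to cause suicidal behavior.** The passages cited above report ideation.

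**Conclusion.** The point holds as a gap in a stated safety rule. In 7.5 and 8.3 the required stop, the risk evaluation and the consultation before restart follow only a new positive C-SSRS question 4 and/or 5. New suicidal behavior and an on-study attempt are not mandatory triggers anywhere in either document.

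Its size in subjects is unknown, and no numeric benefit is claimed. The conclusion rests on the text alone, with one premise: that behavior can come to light, on the C-SSRS or as an adverse event, without a new positive question 4 or 5. The documents neither confirm nor exclude this. If behavior always brought a positive answer to one of those questions, the added words would change nothing.

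Power, type I error and the primary estimate are not in question. This is a low-cost improvement to child safety, not a defect in the efficacy analysis.

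**What to change.** In the trigger sentence of Protocol 7.5, and in the same sentence of 8.3, insert after the reference to questions 4 and/or 5: *or any new suicidal behavior (including a suicide attempt) recorded on the C-SSRS or reported as an adverse event*. Leave the rest of the sentence and the restart sentence unchanged, so that the existing question 4 and 5 rule keeps its present meaning.

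Resolve one ambiguity in the same amendment. The C-SSRS rule calls for immediate discontinuation, while the synopsis and 7.1 say subjects are tapered off at early termination, and Table 2 provides drug for down-titration at that visit. State whether a C-SSRS stop, including one at Week 12, is abrupt or follows the taper. Widening the trigger makes this answer more important.

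The cost is a protocol amendment with IRB/IEC approval across about 60 sites in the United States, Canada and the European Union, plus site notification. A few more subjects may have dosing interrupted, and they can resume under the existing restart sentence. No visit, test or scale is added.

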8. SELECTION AND WITHDRAWAL OF SUBJECTS

8.1. Inclusion Criteria

Individuals must meet all of the following criteria to be included in the study:

- 1) Subject's parent or legal guardian must sign a written informed consent.
- 2) Subject must sign a written informed assent according to the requirements of the site's IRB/EC.
- 3) Subjects must be ≥ 6 to < 18 years of age at time of screening.
- 4) Subjects must weigh ≥ 18 kg (39.6 lbs).
- 5) Subjects must have TS based on Diagnostic and Statistical Manual for Mental Disorders 5th Edition (DSM-5 diagnostic criteria) for TS.
- 6) Subjects must exhibit both motor and vocal tics that cause impairment with normal routines.
- 7) Subjects must have a minimum score of 20 on the YGTSS-TTS at Screening and at Baseline visits with tic symptoms in the Investigator's judgment causing:
 - a. Subjective discomfort (e.g., pain or injury)
 - b. Sustained social problems (e.g., social isolation or bullying)
 - c. Social and emotional problems
 - d. Functional interference (e.g., impairment of academic achievements)
- 8) Subjects may not be taking any medications used to treat motor or vocal tics for at least 14 days prior to Baseline.
- 9) Adolescent females of childbearing potential who are sexually active must be using highly effective contraception (i.e., oral contraceptives, intrauterine device, intrauterine hormone-releasing system, bilateral tubal occlusion, vasectomized male partner) and agree to continue use of highly effective contraception for the duration of their participation in the study. They must also agree to use highly effective contraception for 30 days after their last dose of study drug.
- 10) Sexually active male subjects must use a highly effective method of contraception during the study and agree to continue the use of highly effective contraception for at least 30 days after the last dose of study drug.
- 11) For subjects enrolled outside of the United States and Canada, the subject has received an adequate trial of non-pharmacological therapy without adequate response prior to study enrollment as documented by the Investigator.

8.2. Exclusion Criteria

Individuals meeting any of the following criteria at Screening or Baseline are ineligible to participate in the study:

1) Subjects with any unstable primary mood disorder (DSM-5 criteria) at Screening.

- 2) Subjects who have unstable medical illness or clinically significant abnormalities on laboratory tests, or ECG at Screening as determined by the Principal Investigator.
- 3) Subjects with a significant risk of committing suicide based on history, routine psychiatric status examination, investigator's judgment, or who had an answer of "yes" on any question other than 1–3 (currently or within the past 30 days) on the baseline/screening version of the C-SSRS.
- 4) Subjects with a clinical presentation at Screening and/or history consistent with another neurologic condition that may have had accompanying abnormal movements (e.g., Huntington's disease, Parkinson's disease, Wilson's disease, stroke, Restless Legs Syndrome).
- 5) Female subjects who are currently pregnant or lactating or planning to become pregnant during the course of the study.
- 6) Subjects who have moderate to severe renal insufficiency at Screening.
- 7) Subjects who have hepatic impairment at Screening.
- 8) Subjects with current or recent (past 3 months) history of DSM-5 substance use disorder (with the exception of nicotine).
- 9) Subjects with positive urine drug screen for cocaine, amphetamine, methamphetamine, benzodiazepines, barbiturates, phencyclidine (PCP) or opiates at Screening except those receiving stable, prescribed treatment for ADHD.
- 10) Subjects with \geq 25% absolute change in YGTSS-TTS score between the Screening Visit and Baseline visit assessments.
- 11) Subjects with a lifetime history of bipolar disorder type I or II, dementia, schizophrenia, or any other psychotic disorder.
- 12) Subjects with a major depressive episode in the past 2 years.
- 13) Subjects with a history of attempted suicide.
- 14) Subjects with a history of seizures (excluding febrile seizures that occurred <2 years prior to Screening).
- 15) Subjects with history of neuroleptic malignant syndrome.
- 16) Subjects with a myocardial infarction within 6 months.
- 17) Subjects who have had previous treatment with ecopipam.
- 18) Subjects who have had previous treatment with:
 - a. investigational medication within 1 month prior to Screening
 - b. depot neuroleptics within 3 months prior to Screening
 - c. oral neuroleptics within 4 weeks prior to Screening
- 19) Subjects receiving anti-depressant, anti-anxiety or anti-ADHD medications unless the dosage has been stable for a minimum of 4 weeks prior to Screening and not prescribed to relieve the neurological symptoms related to TS.
- 20) Subjects who have a need for medications which would have unfavorable interactions with ecopipam, e.g., dopamine antagonists or agonists [including bupropion], tetrabenazine, monoamine oxidase inhibitors, or St. John's Wort.
- 21) Initiation or changes in behavioral therapies for TS during the course of the study (i.e., Habit Reversal Training or Comprehensive Behavioral Intervention for Tics) as well as deep brain stimulation.
- 22) Subjects who have initiated new behavior therapies fewer than 10 weeks prior to Baseline visit.

- 23) Subjects unable to swallow tablets.
- 24) Subjects with a known hypersensitivity to ecopipam or any of its excipients.
- 25) Any subject who in the opinion of the investigator is not a suitable candidate for the study.

